13.4.6 Analyses of Exploratory Endpoints

Details of the exploratory analysis of clinical endpoints will be outlined in the SAP. For mechanistic endpoints, exploratory analyses will be conducted separately for subgroups allocated to each Stage 2 treatment arm because participants entering Stage 3 from the different treatment arms are not comparable at the point of re-randomization. Mechanistic plans are to explore baseline (pre-re-randomization) gene expression and protein level patterns among those who respond (or do not respond) to MMF and MMF plus voclosporin, and to describe differences between the 2 arms. Response will be defined using BICLA at 24 weeks post re-randomization.

13.4.7 Descriptive Analyses

Descriptive analyses will include baseline and demographic characteristics, use of medications, and AEs, with separate tables for SAEs, and infections.

Summary statistics for baseline and demographic characteristics, disposition, and medication use will be provided for the mITT and PP populations. These data will be presented in the following manner:

- Continuous data (e.g. age, weight, and height) will be summarized by mean, standard deviation, median, and range.
- Categorical data (e.g. sex and race) will be presented as counts and percentages.

13.5 Interim Analyses

Interim analyses of data will be reported to the DSMB at planned DSMB meetings and as requested by the DSMB.

Planned interim analyses for the DSMB will focus on study conduct and participant safety and may include information on enrollment, randomization, site activation status, major protocol deviations, participant status and demographics, and safety analyses. In addition, the DSMB may review selected disease flare data.

No other interim analyses for futility or efficacy are planned.

13.6 Statistical Hypotheses

The null and alternative hypotheses for the primary analysis of the primary endpoint are defined as follows for the cumulative incidence of treatment failure at Stage 2 Week 24 in the i-th arm and j-th immunologically-defined subgroup, $1 - S_{i,j}(24)$,

$$H_0: S_{MMF,j}(24) = S_{Placebo,j}(24) \text{ for all } j = 1 \text{ to } 7$$
$$H_A: S_{MMF,j}(24) \neq S_{Placebo,j}(24) \text{ for } j \in \{1, \dots, 7\}$$

This hypothesis will be evaluated first for the mITT population pooled over all immunologic cluster. Step-down evaluations will then evaluate the cumulative incidence of treatment failure at Stage 2 Week 24 separately for each cluster.

13.7 Sample Size Considerations

The goal of Stage 2 of the study is to evaluate the potential effectiveness of MMF within previously-identified immunologically-homogeneous clusters of lupus patients. To place these cluster comparisons in the context of a successful trial, target enrollment is based on power to show superiority of MMF over placebo in a pooled lupus population.

In previous studies using BOLD designs in lupus populations [22, 93, 94] where long-acting corticosteroids were administered during the treatment withdrawal stage, survival free-from-failure at 6 months in untreated or placebo-treated participants ranged from 5-20% [25]. These studies included participants with a range of disease activity, had differing rules on implementation of background steroids and different definitions for treatment failure. By limiting steroids and carefully adhering to entry criteria to recruit an appropriate population with active lupus disease activity, and by defining treatment failure to include individuals who receive rescue medications post-randomization or who withdraw from treatment prematurely, a placebo survival at 24 weeks of 15% or less should be achievable. In the MMF arm, a minimum clinically meaningful improvement would be 35% survival at 24 weeks.

A study design with 120 participants randomized 1:1 to placebo or MMF will have between 74% to \geq 95% power if placebo survival at Stage 2 Week 24 ranges from 15% to 10% and MMF survival at Stage 2 Week 24 ranges from 35% to 50% (2-sided, $\alpha=0.05$); power is \geq 80% when MMF survival at Stage 2 Week 24 is at least 37%. Power for a two-sample landmark analysis was computed for a Z-Test with unpooled variance using binomial enumeration.

In addition, a simulation study was conducted to determine the power for the supportive analysis using log-rank tests for time until treatment failure under assumptions of non-constant and non-proportional hazards based on the results of previous studies using BOLD designs in lupus populations [22, 93, 94]. Specifically, under an assumption the baseline hazard doubles at Week 12 with an attenuation of long-acting corticosteroids, a proportional hazard corresponding to an increase in survival at Stage 2 Week 24 from 15% to 35% with MMF (HR = 0.55) results in 80.0% power. When all treatment benefit from MMF is restricted to after Week 12, power of the log-rank test decreases to 61.3%, but there remains power to detect larger treatment effects (power = 87.9% when SMMF,24 = 45% and SPlacebo,24 = 15%).

The baseline immunologic cluster would be a useful marker for identifying individuals with a propensity to respond to MMF if some clusters have a very poor response and others have a large response. Hence, the by-cluster comparisons are powered to identify clusters with an MMF response of 60-80% survival at Stage 2 Week 24, which is well above that expected for the overall population.

Table 13.1 gives the number required per arm in a given cluster to achieve 80% power to detect large differences in survival over 24 weeks between arms (based on log-rank test, $\alpha=0.1$, 2-sided). For example, if the underlying placebo survival is 10% at 24 weeks, then 6-9 per arm within a given cluster gives 80% power to detect survival in the MMF arm ranging from 60-80%. Power for within-cluster comparisons will be maximized if numbers per arm are equal. Although stratifying randomization by baseline cluster assignment (7 clusters) is not feasible, stratification by gene expression signature (3 levels) serves as a first-cut approximation to the cluster assignment and should facilitate balance between arms.

Table 13.1. Cluster comparisons: # per arm to achieve 80% power on comparison of survival over 24 weeks

		*Survival at Stage 2 Week 24: MMF				
		60%	65%	70%	75%	80%
*Survival at Stage 2 Week 24: Placebo	5%	7	6	6	5	5
	10%	9	8	7	6	6
	15%	13	11	9	8	7

* Assumed underlying %survival in the population of MMF (or placebo) -treated patients.

Although the number per cluster will be random, if the 7 clusters are evenly distributed in the lupus population, then the number achieved for any given cluster will likely include 11 to 24 individuals (i.e. $> 90\%$ chance) or approximately 5 to 12 per arm. Hence, we are likely to have adequately powered comparisons for at least some clusters.

For Stage 3, we anticipate that at least 48 (80%) among those randomized to placebo in Stage 2 and approximately 36 (60%) among those randomized to MMF in Stage 2 will be eligible for re-randomization to MMF or MMF plus voclosporin. For Stage 3 analyses, we will have 4 groups defined by the cross-classification of Stage 2 and Stage 3 treatment assignments, as follows:

Stage 2 Randomization

Stage 3 Re-randomization	MMF	Placebo MMF
MMF + voclosporin	n_{MMF_Combo} (~18)	$n_{placebo_Combo}$ (~24)
MMF + placebo voclosporin	n_{MMF_MMF} (~18)	$n_{placebo_MMF}$ (~24)

Stage 3 is intended to explore baseline (pre-re-randomization) gene expression patterns and their associations with response (or non-response) to MMF and MMF plus voclosporin, and to describe differences in those associations between the 2 arms. Gene expression patterns may include immunologically-homogeneous clusters defined at screening, gene expression at the Stage 2 Day 0 Randomization Visit, or differential expression observed during the Stage 2 treatment period. Among those randomized to placebo in Stage 2, if we re-randomize 24 to MMF, we anticipate 8-12 responders (i.e. 35-50% who have not failed by Stage 2 Week 24) and 12-16 non-responders on which to evaluate baseline gene expression patterns. In the MMF plus voclosporin arm, the number of responders is expected to be at least as high as MMF alone. Stage 3 is exploratory and not powered to test a pre-specified hypothesis.

14 Identification and Access to Source Data

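### Section 13.7: the >90% probability for cluster size does not carry over to the per-arm range, and the 60-80% power claim fails for MMF survival of 60-65% when placebo survival is 15%

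*Combined protocol and SAP*

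**What the plan says.** All of this is in the combined protocol and SAP, Section 13.7. The sample size is set by the pooled comparison: "A study design with 120 participants randomized 1:1 to placebo or MMF". For the clusters, the plan states that "the by-cluster comparisons are powered to identify clusters with an MMF response of 60-80% survival at Stage 2 Week 24", and that sentence names no placebo rate. Table 13.1 then lists the number per arm for 80% power ("based on log-rank test, $\alpha=0.1$, 2-sided") at placebo survival of 5, 10 and 15%.

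On cluster size, the plan assumes that all seven are equally common and argues that "the number achieved for any given cluster will likely include 11 to 24 individuals", with a probability above 90%. It restates this as "or approximately 5 to 12 per arm. Hence, we are likely to have adequately powered comparisons for at least some clusters".

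On balance, it says: "Although stratifying randomization by baseline cluster assignment (7 clusters) is not feasible", but that "stratification by gene expression signature (3 levels) serves as a first-cut approximation to the cluster assignment and should facilitate balance between arms".

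**The concern.** Two separate statements are at issue.

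- **The per-arm range.** Dividing 11-24 by two gives about 5-12 only if each cluster splits almost evenly between arms. The plan says it cannot stratify on cluster, so each arm's count has its own variation, and the probability attached to the total does not carry over.
- **The power claim.** Section 13.7 plans on placebo survival of 15% or less. At 15% and MMF 60%, Table 13.1 asks for 13 per arm, which is already above the plan's own upper figure of 12. The table therefore contradicts an unqualified claim of power from 60% upwards.

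The stake is how a cluster without a notable result is read. Section 13.4.2 makes within-cluster evaluation the ultimate aim of Stage 2 and runs these tests whatever the pooled result. It mentions limited sample sizes and warns about false positives, but does not say what a non-notable cluster means. If the comparisons are described as powered, such a cluster may be taken as one in which MMF does not work.

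**Working it through.** **Inputs (Section 13.7).** N = 120, 60 per arm; seven clusters of equal prevalence, so p = 1/7 and a mean of 120/7 = 17.1 per cluster, or 8.6 per arm; log-rank test, two-sided alpha 0.10; Table 13.1 sizes.

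**1. The plan's own figures.** For X ~ Binomial(120, 1/7), P(11 ≤ X ≤ 24) = 93.3%, so the stated figure reproduces. Table 13.1 also holds up: simulated log-rank power at the listed sizes is 82-89%.

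**2. Per-arm range.** With 60 per arm and no cluster balance, each arm's count is Binomial(60, 1/7). P(5 ≤ count ≤ 12) = 0.864 for one arm, and 0.864² = 74.6% for both. The documents do not map the seven clusters to the signature strata, so partial balance is shown as a range (cluster split hypergeometrically within a balanced stratum):

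- stratum holds 4 whole clusters: 76.7%
- stratum holds 3: 78.5%
- stratum holds 2: 82.3%
- the cluster itself balanced: 95.1%

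**3. Reaching the Table 13.1 sizes.** With no cluster balance, the chance that both arms of a given cluster reach n is P(Binomial(60, 1/7) ≥ n)². With perfect halving it is P(Binomial(120, 1/7) ≥ 2n). The chance that at least one of the seven clusters reaches n comes from multinomial simulation. Power is simulated log-rank power under proportional hazards.

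| Placebo / MMF survival | n per arm | Both arms reach n | Same, perfect halving | At least one of 7 | Power, arms of 8 and 9 | Mean power over random split |
|---|---|---|---|---|---|---|
| 15% / 60% | 13 | 0.6% | 1.8% | 4.3% | 68% | 65% |
| 15% / 65% | 11 | 5.4% | 13% | 35% | 76% | 72% |
| 15% / 70% | 9 | 24% | 45% | 92.6% | 82% | 78% |
| 15% / 80% | 7 | 60% | 83% | about 100% | 92% | 89% |
| 10% / 60% | 9 | 24% | 45% | 92.6% | 80% | 77% |
| 10% / 70% | 7 | 60% | 83% | about 100% | 90% | 87% |
| 5% / 60% | 7 | 60% | 83% | about 100% | 91% | 88% |

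With equal arms of 8 or 9, power is about 65-70% for 15% versus 60%, and about 77-82% for 10% versus 60%.

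**4. Cause of the shortfall.** Under perfect halving, 13 and 11 per arm are still reached only 1.8% and 13% of the time. Cluster size is the main limit; uneven splitting makes it worse.

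**5. The rest of the table.** Nine of the 15 cells need 7 or fewer per arm (five at 5% placebo, three at 10%, one at 15%). A given cluster reaches those sizes 60% (n = 7) to 89% (n = 5) of the time with no cluster balance. Thirteen of the 15 need 9 or fewer, and at least one cluster then qualifies with probability 92.6% or more.

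**The case against.** The plan is fairly open on this. It says that the number per cluster is random, calls the per-arm range approximate, says that clusters cannot be strata, and expects the signature strata to help. Its conclusion is modest: some clusters, not all. The 15% placebo figure is the top of the planning assumption and the least favourable row of Table 13.1; the worked example uses 10%. Missing a listed size by one or two is also not a collapse in power, since the table is slightly conservative. At 10% versus 60%, only 24% of clusters reach 9 per arm, yet power with 8-9 per arm is about 77-82%. Nothing in the documents says that a non-notable cluster is one where MMF fails, and N is fixed by the pooled comparison.

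Most of this stands, and it rules out three stronger readings that a reader might infer:

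- **That most clusters cannot reach the sizes required.** This is untrue for the nine cells needing 7 or fewer per arm.
- **That the conclusion about at least some clusters is wrong.** It fails only for the two cells needing 11 and 13. It does, however, count any cluster that is large enough, which need not be the one where MMF works.
- **That arm imbalance explains the low power.** Cluster size does so mainly, and some balance through the strata is likely.

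The objection does not rescue the two statements themselves. The probability above 90% does not describe the per-arm range, and the power claim carries no placebo condition although the plan allows 15%.

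**Conclusion.** The point holds in limited form. The per-arm range has a probability of about 75-82%, against 93.3% for the cluster total. The claim of power for 60-80% MMF survival is supported at 5-10% placebo survival (about 80% at the 10% versus 60% margin) and for about 70-80% MMF survival at 15% placebo. It is not supported for MMF 60-65% at 15% placebo, where power with 8-9 per arm falls below 80% and the required sizes are almost never met.

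This rests on equal cluster prevalence (the plan's own assumption), no dropout and proportional hazards. It also uses the log-rank test on which Table 13.1 is based; Section 13.4.2 names a landmark two-sample test for the clusters, which was not evaluated here. Unequal prevalence would make some clusters larger and others smaller than shown.

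**What to change.** In Section 13.7:

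1. Keep the probability above 90% for the cluster total, and state separately that both arms are expected to fall in 5-12 about 75-82% of the time, depending on how far the signature strata track the clusters.
2. Limit the power claim to what 8-9 per arm support: MMF survival of 60-80% at placebo 5-10%, and about 70-80% at placebo 15%. State that MMF 60-65% at placebo 15% has less than 80% power.
3. Say, there or in Section 13.4.2, that a cluster without a notable result is inconclusive and is not evidence that MMF has no effect in it.

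The cost is wording and a slightly less favourable stated figure. Sample size, randomization and analysis do not change.

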14.1 Source Data

Source documents and source data are considered to be the original documentation where participant information, visits consultations, examinations and other information are recorded. Documentation of source data is necessary for the reconstruction, evaluation and validation of clinical findings, observations and other activities during a clinical trial.

14.2 Access to Source Data

The site investigators and site staff will make all source data available to the DAIT/NIAID, NIAID representatives, agents, employees, contractors, and other persons assisting in conducting, monitoring, or analyzing the study, as well as to relevant health authorities. Authorized representatives, as noted above, are bound to maintain the strict confidentiality of medical and research information that may be linked to identify individuals.

15 Quality Assurance and Quality Control

The PI is required to keep accurate records to ensure that the conduct of the study is fully documented. The PI is required to ensure that all eCRFs are completed for every participant entered in the trial. The period of record retention should be consistent with the record retention policies of the sponsoring agency or applicable regulatory agencies. However, in certain instances, documents should be retained for a longer period if required by the applicable regulatory agency or by the National Institutes of Health (NIH).

Data will be obtained from a variety of sources including, but not limited to laboratory notebooks, automated instrument output files, and clinical participant charts. Data from these source materials will be transmitted to the DAIT data center via one of two mechanisms. Data collected electronically at central laboratories will be transferred electronically directly from the laboratory to the DAIT data center using standard secure data transfer procedures. Data collected at the clinical site will be transmitted to the DAIT data center using an internet-based remote data entry system. Clinical site personnel use an internet browser to key data into eCRFs; each CRF page is submitted to the clinical

database electronically as the page is completed. Univariate data validation tests are performed as the data are keyed. The clinical database is backed up nightly; backup tapes are saved in a secure, off-site location. At any time, authorized site personnel may log in to the remote data entry system, review and correct previously entered data, or key additional data. The data will be further validated per the study data validation plan via a series of computerized and manual edit checks, and all relevant data queries will be raised and resolved on an ongoing basis. Complete, clean data will be frozen to prevent further inadvertent modifications. All discrepancies will be reviewed and any resulting queries will be resolved with the investigators and amended in the database. All elements of data entry (i.e., time, date, verbatim text, and the person performing the data entry) will be recorded in an electronic audit trail to allow all data changes in the database to be monitored and maintained in accordance with federal regulations.

Monitors are responsible for regular inspection of the conduct of the trial, for verifying adherence to the protocol, and for confirming the completeness, consistency, and accuracy of all documented data.

Monitors will periodically visit the participating clinical site and audit the source documents in order to validate the data in the central database. Data will be provided using the participants screening or enrollment number, the DAIT data center will not collect personally identifying information such as the participants name or social security number. Participants will provide demographic information such as race, ethnicity, and birth date.

Data collected by the DAIT data center will be held in the strictest confidence and are protected from access that could reveal personally identifying information about any participant in the trial.

16 Protocol Deviations

16.1 Protocol Deviation Definitions

Protocol Deviation – The investigators and site staff will conduct the study in accordance to the protocol; no deviations from the protocol are permitted. Any change, divergence, or departure from the study design or procedures constitutes a protocol deviation. As a result of any deviation, corrective actions will be developed by the site and implemented promptly as appropriate.

Major Protocol Deviation (Protocol Violation) - A Protocol Violation is a deviation from the IRB-approved protocol that may affect the participant's rights, safety, or well-being and/or the completeness, accuracy and reliability of the study data. In addition, protocol violations include willful or knowing breaches of human subject protection regulations, or policies, any action that is inconsistent with the NIH Human Research Protection Program's research, medical, and ethical principles, and a serious or continuing noncompliance with federal, state, local or institutional human subject protection regulations, policies, or procedures.

Non-Major Protocol Deviation - A non-major protocol deviation is any change, divergence, or departure from the study design or procedures of a research protocol that does not have a major impact on the participant's rights, safety or well-being, or the completeness, accuracy and reliability of the study data.

16.2 Reporting and Managing Protocol Deviations

The study site PI has the responsibility to identify, document and report protocol deviations as directed by DAIT/NIAID. However, protocol deviations may also be identified during site monitoring visits or during other forms of study conduct review.

When a deviation occurs, corrective actions may be necessary depending on the nature of the deviation. Risk assessment must occur by the investigator and study sponsor. The investigator should ensure a procedure for the timely correction and documentation of problems identified by study personnel, outside monitors or auditors, or other parties involved in the conduct of a study. The depth of Corrective Action/Preventive Action (CAPA) required should match the risk and impact on safety of participants and/or the quality of the data.

Upon determination that a protocol deviation has occurred, the investigator/designated study staff will report the deviation according to the processes outlined for the study. A major deviation is to be reported within 3 business days and reported by the investigator to the IRB per IRB reporting requirements. The study sponsor will determine reportability of the deviation to the DSMB as applicable.

17 Ethical Considerations and Compliance with Good Clinical Practice

17.1 Statement of Compliance

This clinical study will be conducted using good clinical practice (GCP), as delineated in Guidance for Industry: E6 Good Clinical Practice Consolidated Guidance, and according to the criteria specified in this study protocol. Before study initiation, the protocol and the informed consent documents will be reviewed and approved by the IRB. Any amendments to the protocol or to the consent materials will also be approved by the IRB before they are implemented.

17.2 Informed Consent Process

The consent process will provide information about the study to a prospective participant and will allow adequate time for review and discussion prior to his/her decision. The investigator or designee listed on the IORA will review the consent and answer questions. The prospective participant will be told that being in the trial is voluntary and that he or she may withdraw from the study at any time, for any reason. All participants (or their legally acceptable representative) will read, sign, and date a consent form before undergoing any study procedures. Consent materials will be presented in participants' primary language. A copy of the signed consent form will be given to the participant.

The consent process will be ongoing. The consent form will be revised when important new safety information is available, the protocol is amended, and/or new information becomes available that may affect participation in the study. The consent/assent process will be documented in the research or medical records.

